### **11.7 Publication Policy**

Following completion of the study, the data may be considered for publication in a scientific journal or for reporting at a scientific meeting. Each Investigator is obligated to keep data pertaining to the study confidential. The Investigator must consult with the Sponsor before any study data are submitted for publication. The Sponsor reserves the right to deny publication rights until mutual agreement on the content, format, interpretation of data in the manuscript, and journal selected for publication are achieved.

### **11.8 Financial Disclosure**

Clinical Investigators are required to provide financial disclosure information to the Sponsor to permit the Sponsor to fulfill its obligations under 21 CFR §54. In addition, Investigators must commit to promptly updating this information if any relevant changes occur during the study and for a period of 1 year after the completion of the study.

### **11.9 Insurance and Indemnity**

In accordance with the relevant national regulations, the Sponsor has taken out clinical trial insurance. This insurance provides coverage to the Sponsor in the event of physical injury or death related to the study drug or any procedure related to the protocol.

### **11.10 Legal Aspects**

The clinical study is submitted to the relevant national competent authorities in all participating countries to achieve a clinical trial authorization (CTA).

The study will commence (i.e., initiation of study centers) when the CTA and favorable Ethics opinion have been received.

### **11.11 Definition of End of Study**

The End of Study is defined as the completion of the Follow-up Visit or the ET Visit, if applicable.

### **11.12 Sponsor Discontinuation Criteria**

Premature termination of this study may occur because of a regulatory authority decision, change in opinion of the IRB/EC, drug safety problems, or at the discretion of Gemphire. In addition, Gemphire retains the right to discontinue development of gemcabene at any time.

If a study is prematurely terminated or discontinued, Gemphire will promptly notify the Investigator. After notification, the Investigator must contact all participating subjects within 2 weeks. As directed by Gemphire, all study materials must be collected and all eCRFs completed to the greatest extent possible.

## **12 STUDY ADMINISTRATIVE INFORMATION**

### **12.1 Protocol Amendments**

Any amendments to the study protocol will be communicated to the Investigators by **PI** [REDACTED] or the Sponsor. All protocol amendments will undergo the same review and approval process as the original protocol. A protocol amendment may be implemented only after it has been approved by the IRB/REB, unless immediate implementation of the change is necessary for subject safety. In this case, the situation must be documented and reported to the IRB within 5 working days.

## APPENDIX A: SCHEDULE OF PROCEDURES

	Pre-Screening a	Screening b,f				Treatment Period c				Follow-Up d	ET
		Study Day -28 to -21	Study Day -14 to -7	Study Day-7	Study Day 1 e	Week 2/ Study Day 15±3 days	Week 6/ Study Day 43±3 days	Week 10/ Study Day 71±3 days	Week 12/ Study Day 85 or up to 3 days prior to Study Day 85	Study Day 113	
	Visit Identifier	Visit S1	Visit S2	Visit S3	Visit T1	Visit T2	Visit T3	Visit T4	Visit T5	Visit FU1	
Informed consent	X	X									
Inclusion/exclusion criteria	X	X	X	X	X						
Medical/surgical history and demographics	X	X	X	X	X						
Full physical examination g	X	X							X		X
Symptom-directed physical examination		X h			X	X	X	X		X i	
Vital signs j , height k , and weight	X	X	X	X	X	X	X	X	X		X
Body Mass Index (BMI)	X	X			X			X	X		X
Waist circumference					X				X		X
Urinalysis + NAGL l	X	X			X		X		X	X i	X
Protein:creatinine ratio; albumin:creatinine ratio	X	X			X		X		X	X i	X
Serum/urine pregnancy test m	X	X			X	X	X	X	X	X i	X
Safety chemistry panel, coagulation, and hematology n	X	X	X	X	X	X	X	X	X	X i	X
TSH and serology o	X	X f									
Fasting lipid panel p	X q	X	X	X	X	X	X	X	X	X	X
Fasting apolipoproteins r					X			X	X	X	X
LDL-C ultracentrifugation (LDL-C, LDL-TG, VLDL-TG)					X			X	X	X	X
Cl ██████████					X				X		X
HbA1c	X	X			X				X		X
Cystatin-C, ANGPTL4, adiponectin					X				X		X

hsCRP, SAA, IL-6, and fibrinogen					X			X	X		X
Lipoprotein size and particle number					X				X		X
Randomization					X						
Study drug administration s					X	X	X	X			
Dispense study drug and instructions					X	X	X	X			
Compliance check						X	X	X	X		X
Distribute drug diary					X	X	X	X			
Dietary assessment (self-reported) t	X	X	X	X	X	X	X	X			
12-lead ECG u		X			X	X	X	X	X		X
Initiate wash-out	X										
Adverse events	X v	X v	X	X	X	X	X	X	X	X	X
Concomitant medications	X	X f	X	X	X	X	X	X	X	X	X
Reserve serum samples w					X	X	X	X	X		X
Reserve plasma PK samples x					X	X	X	X	X		X
Collect drug diary						X	X	X	X		X
Reserve genotyping sample					X						

Footnotes appear on the following page

- a. Only subjects requiring a Wash-Out Period will participate in the Pre-Screening Visit. Specifically, PCSK9 inhibitors will require an 8-week Wash-Out Period, fibrates will require a 6-week Wash-Out Period, and niacins, OMG-3, bile acid sequestrants or other lipid-regulating therapies will require a 4-week Wash-Out Period, prior to the Screening Visit.
- b. All eligible subjects will participate in the Screening Visit up to 28 days prior to Study Day 1. For subjects taking the required stable statin therapy for >12 weeks at the Screening Visit and do not require a Wash-Out Period, the Screening Visit will be their first study visit.
- c. Study assessments will be completed  $\pm 3$  days of given time point for all study visits from Study Day 1 through Week 10. Week 12 assessments can be performed up to 3 days prior to Study Day 85, but not after Study Day 85.
- d. The Follow-up Visit will be conducted as a telephone call 4 weeks ( $\pm 3$  days) after the last dose of study drug, unless the subject requires a site visit due to an abnormal result at Week 12 (or the ET Visit, if applicable) or an ongoing treatment-related adverse event.
- e. Procedures will be performed pre-dose. The Investigator will inquire with the subject at Study Day 1 to determine if there have been any changes in the subject's health affecting eligibility or requiring an update to their medical and surgical history.
- f. For subjects who required a Wash-Out Period and completed the Pre-Screening Visit, the following Screening Visit procedures will not be repeated: informed consent, full physical examination, height, TSH, HbA1c, and serology (HBV, HCV, and HIV) screening. Updates, as needed, will be made to medical/surgical history, demographics, and concomitant medications.
- g. A full physical examination includes genitourinary examination per the Investigator's discretion and does not include a rectal examination.
- h. Only for subjects who required a Wash-Out Period and completed the full physical examination at the Pre-Screening Visit.
- i. Only for subjects who had an abnormal result at Week 12 (or the ET Visit, if applicable) or an ongoing treatment-related adverse event.
- j. Vital signs include pulse rate, blood pressure, respiration rate, and temperature. Blood pressure should be obtained in the seated position, after the subject has rested comfortably for at least 5 minutes. Blood pressure at the Screening Visit should be obtained in both arms and the arm with the highest value should be used for ongoing monitoring throughout the rest of the study. If an automated assessment is performed, the same machine should be used for the subject throughout the study when possible. Care should be taken to ensure an appropriate cuff size is utilized.
- k. Height will be measured only at the subject's first study visit, either at the Pre-Screening Visit or the Screening Visit.
- l. Urine will be collected for a full urinalysis at the lab including protein:creatinine ratio and albumin:creatinine ratio at the Prescreening/screening Visit, Study Day 1, Week 6, Week 12, the Follow-up Visit (only for subjects who had an abnormal result at Week 12 [or the ET Visit, if applicable] or an ongoing treatment-related adverse event), and the ET Visit, if applicable. Urinary NGAL will be measured at Study Day 1, Week 6, Week12, the Follow-up Visit (only for subjects who had an abnormal result at Week 12 [or the ET Visit, if applicable] or an ongoing treatment-related adverse event), and the ET Visit, if applicable.
- m. For women of child-bearing potential only, a serum pregnancy test will be conducted at the Screening Visit, Week 12, and the ET Visit, if applicable. A urine pregnancy test will be conducted at the Pre-Screening Visit, Study Day 1, Week 2, Week 6, and Week 10.
- n. Clinically significant abnormal creatinine results at Week 12 (or the ET Visit, if applicable) will also be followed-up 2 weeks ( $\pm 3$  days) after the last dose of study drug in addition to the 4 week ( $\pm 3$  days) Follow-up Visit. See [Appendix B](#) for a list of analytes and description of when repeat or reflexive testing will be required.
- o. Thyroid-stimulating hormone, HbA1c, and serology (HBV, HCV, and HIV) will be measured at the subject's first study visit, either at the Pre-Screening Visit, if applicable, or the Screening Visit.
- p. Includes non-HDL-C, TC, TG, HDL-C, and VLDL-C and HDL-TG. Fasting will be defined as no food or caloric beverage for at least 10 hours prior to sample collection. Subjects will be permitted to have water, black tea or black coffee.
- q. Includes TG only. Fasting will be defined as no food or caloric beverage for at least 10 hours prior to sample collection. Subjects will be permitted to have water, black tea or black coffee.
- r. Includes ApoB, ApoA-I, ApoA-II, ApoA-V, ApoC-II, ApoC-III, and ApoE. Fasting will be defined as no food or caloric beverage for at least 10 hours prior to sample collection. Subjects will be permitted to have water.
- s. Study drug will be administered at the site on Study Day 1. Subjects will self-dose at all other times during the Treatment Period.
- t. Subjects will self-report compliance to a stable, heart-healthy diet.
- u. Subjects should be lying quietly in a fully supine position for at least 10 minutes prior to each 12-lead ECG.

- v. Serious adverse events that occur prior to the first dose of study drug (Study Day 1) should be reported as an update to medical history as well as be reported on the appropriate adverse event eCRF.
- w. The following may be analyzed: RLP-C, RLP-TG and RLP-apoB, Lp(a), ox-LDL, and Lp-PLA2.
- x. Plasma samples collected at Week 2, Week 6, Week 10, Week 12 and ET will be used for the analysis of gemcabene PK. The plasma sample collected at Day 1 will be reserve.

Apo = apolipoprotein; ECG = electrocardiogram; eCRF = electronic case report form; ET = Early Termination; HBV = hepatitis B virus; HbA1c = hemoglobin A1c; HCV = hepatitis C virus; HDL-C = high-density lipoprotein cholesterol; HIV = human immunodeficiency virus; HoFH = homozygous familial hypercholesterolemia; hsCRP = high-sensitivity C-reactive protein; LDL-C = low-density lipoprotein cholesterol; Lp(a) = lipoprotein(a); NCEP ATP-III = National Cholesterol Education Program Adult Treatment Panel III; NGAL = neutrophil gelatinase-associated lipocalin; non-HDL-C = non-high-density lipoprotein cholesterol; TC = total cholesterol; TG = triglyceride; TSH = thyroid-stimulating hormone; VLDL-C = very low-density lipoprotein cholesterol.

## APPENDIX B: CLINICAL LABORATORY ANALYTES

### Standard Safety Chemistry Panel

Alanine aminotransferase	Albumin
Alkaline phosphatase	Aspartate aminotransferase
Bicarbonate	Blood urea nitrogen
Calcium	Chloride
Creatine kinase	Creatinine [1]
Gamma-glutamyl transferase	Glucose
Lactate dehydrogenase	Phosphorus
Potassium	Sodium
Total bilirubin [2]	Total protein
Estimated glomerular filtration rate (GFR) [3]	

1. For a creatinine increase of  $>0.3$  mg/dL (27  $\mu$ mol/L) from baseline during the study, repeat chemistry will be performed.
2. If total bilirubin is elevated, reflexive direct bilirubin testing will be performed.
3. For an estimated GFR decrease of  $>15$  mL/min from baseline during the study, repeat chemistry will be performed.

### Additional Chemistry Parameters

Cystatin-C
Fasting plasma glucose
HbA1c
Fasting insulin

### Endocrinology

Thyroid-stimulating hormone
-----------------------------

### Hematology

Hematocrit	Hemoglobin [1]
Platelet count	Red blood cell count
Mean corpuscular hemoglobin concentration	Mean corpuscular hemoglobin
White blood cell count and differential (basophils, eosinophils, lymphocytes, monocytes, and neutrophils) [2]	Mean corpuscular volume

1. For a hemoglobin decrease of  $>1.5$  g/dL from baseline during the study, repeat hematology studies and reflexive evaluation of reticulocyte count will be performed.
2. Manual microscopic review is performed only if white blood cell count and/or differential values are out of reference range.

## Urinalysis [1]

pH	Proteinuria [2]
Ketones	Blood
Leukocyte esterase	Specific Gravity
Glucose	Bilirubin
Nitrite	Neutrophil gelatinase-associated lipocalin (NGAL) [3]
Albumin	

1. A urine microscopic examination will be performed when dipstick results are abnormal (positive for blood, leukocyte esterase, or nitrites).
2. Urine protein:creatinine ratio will be performed at the Screening Visit, Study Day 1, Study Day 28, Study Day 85, the Follow-up Visit (only for subjects who had an abnormal result at Study Day 85 [or the ET Visit, if applicable] or an ongoing treatment-related adverse event), and the ET Visit, if applicable.
3. Urine protein:creatinine ratio will be performed at the Screening Visit, Study Day 1, Study Day 28, Study Day 85, the Follow-up Visit (only for subjects who had an abnormal result at Study Day 85 [or the ET Visit, if applicable] or an ongoing treatment-related adverse event), and the ET Visit, if applicable.
4. Urinary NGAL will be measured at Study Day 1, Study Day 28, Study Day 85, the Follow-up Visit (only for subjects who had an abnormal result at Study Day 85 [or the ET Visit, if applicable] or an ongoing treatment-related adverse event), and the ET Visit, if applicable.

## Pregnancy Test

Serum and urine pregnancy tests will be administered to all female subjects of child-bearing potential.

## Serology

Hepatitis B	Hepatitis C
Human Immunodeficiency Virus	

## Coagulation

Prothrombin time	Activated partial thromboplastin time
International normalized ratio	

## Efficacy Parameters

The following efficacy parameters will be assessed in this study:

Apo A-I	ApoA-II
ApoB	ApoC-II
ApoA-V	ApoC-III
Triglycerides	ApoE
High-density lipoprotein cholesterol	Low-density lipoprotein cholesterol
Non-high-density lipoprotein cholesterol	Very low-density lipoprotein cholesterol
SAA	Total cholesterol
High-sensitivity C-reactive protein	IL-6
ANGPTL4	Fibrinogen

## APPENDIX C: NEW YORK HEART ASSOCIATION CONGESTIVE HEART FAILURE CLASSIFICATION

- Class I: subjects with cardiac disease but without resulting limitation of physical activity. Ordinary physical activity does not cause undue fatigue, palpitation, dyspnea, or anginal pain.
- Class II: subjects with cardiac disease resulting in slight limitation of physical activity. They are comfortable at rest. Ordinary physical activity results in fatigue, palpitation, dyspnea, or anginal pain.
- Class III: subjects with cardiac disease resulting in marked limitation of physical activity. They are comfortable at rest. Less than ordinary activity causes fatigue, palpitation, dyspnea, or anginal pain.
- Class IV: subjects with cardiac disease resulting in inability to carry on any physical activity without discomfort. Symptoms of heart failure or the anginal syndrome may be present even at rest. If any physical activity is undertaken, discomfort is increased.

Source: The Criteria of the New York Heart Association. Nomenclature and Criteria for Diagnosis of the Heart and Great Vessels. 9th ed. Boston, Mass: Little, Brown & Co; 1994:253-256.

## APPENDIX D: REFERENCE LIST OF CYTOCHROME P450 3A4 INHIBITOR EXCLUSIONARY MEDICATIONS

Amiodarone	Amprenavir
Atazanavir	Cimetidine
Clarithromycin	Conivaptan
Darunavir	Delavirdine
Diltiazem	Erythromycin
Fluconazole	Fluvoxamine
Fosamprenavir	Grapefruit juice
Imatinib	Indinavir
Itraconazole	Ketoconazole
Lopinavir	Miconazole
Mibepradil	Nefazodone
Nelfinavir	Posaconazole
Ritonavir	Saquinavir
Telithromycin	Tipranavir
Troleandomycin	Verapamil
Voriconazole	

## APPENDIX E: MUSCLE INJURY AND HEPATIC MONITORING

### Muscle Injury

Muscle injury will be assessed using a combination of clinical signs and symptoms and laboratory data (creatinine kinase [CK], hepatic, and renal function).

All subjects with suspected or confirmed muscle injury should be managed according to the standard of care at the discretion of the Investigator.

- Subjects with new or unexplained muscle symptoms should have an unscheduled visit scheduled within 7 days of site notification. At this visit, samples should be sent for a full chemistry panel, including CK, liver, and renal function.
- Subjects with CK elevations of  $>3 \times$  upper limit of normal (ULN) who are asymptomatic should be considered for an unscheduled visit (+ isozymes), based upon medical judgment.
- All subjects with CK elevations  $>10 \times$  ULN should have an unscheduled visit (+ isozymes). Study drug should be temporarily discontinued, pending the results of an investigation into the cause of muscle injury and/or CK elevation is complete.

It is important that subjects are instructed to not undertake any form of strenuous physical activity for at least 24 hours prior to repeat blood testing.

### Hepatic Monitoring

Subjects with hepatic enzyme elevations should be managed according to the standard of care, at the discretion of the Investigator. For subjects with signs or symptoms suggestive of hepatitis, an unscheduled visit and a chemistry panel should be performed. Subjects with an alanine aminotransferase (ALT)  $>2 \times$  ULN with symptoms suggestive of hepatitis should have an unscheduled visit. Subjects with ALT  $>3 \times$  ULN with or without symptoms should also have an unscheduled visit. A repeat assessment should be performed as soon as possible to confirm the finding. A clinical evaluation should be performed, including assessment of past medical history (including non-alcoholic fatty liver disease/steatohepatitis and alcohol use) and concomitant medications (including over the counter drugs and herbal supplements). Risk factors for hepatitis infection should be reviewed and hepatitis studies should be performed.

Study drug should be temporarily discontinued during this evaluation if the subject has signs or symptoms of hepatitis or an ALT  $>5 \times$  ULN. The possible dosing re-initiation (re-challenge) or follow-up schedule for any events meeting these criteria will be determined by the Investigator in consultation with the Medical Monitor.

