### 4.2 Exclusion Criteria

Subjects who meet any of the following criteria will be excluded from participation in the study. Subjects may re-screen once if they were previously excluded from the study based on criteria that has now been altered by Amendment #3.

1. Known and previously documented homozygous genetic deficiencies (LPL, ApoC-II, ApoC-III, ApoA-V, GPIHBP1, or LMF1);
2. History of pancreatitis within the last 6 months prior to screening (Visit S1);

3. History of bariatric surgery; symptomatic gallstone disease, unless treated with cholecystectomy;
4. Abnormal liver function test at the Pre-Screening Visit or any of the Screening Visits (aspartate aminotransferase or alanine aminotransferase  $> 2 \times$  the upper limit of normal [ULN], total bilirubin  $> 1.5 \times$  ULN, or alkaline phosphatase  $> 2 \times$  ULN based on appropriate age and gender normal values). Subjects with bilirubin  $> 1.5 \times$  ULN and history of Gilbert's syndrome may be included; reflexive direct bilirubin testing will be used to confirm Gilbert's syndrome;
5. Creatine kinase (CK) at the Pre-Screening Visit or any of the Screening Visits  $> 3 \times$  ULN and/or unexplained muscle pain, tenderness or weakness;
6. Active liver disease (e.g., cirrhosis, alcoholic liver disease, hepatitis B [HBV], hepatitis C [HCV], autoimmune hepatitis, liver failure, liver cancer), history of liver transplant, known diagnosis of human immunodeficiency virus (HIV), or acquired immune deficiency virus;
7. Moderate to severe renal insufficiency defined as an estimated GFR  $< 60$  mL/min/1.73 m^2 (calculated using The Chronic Kidney Disease Epidemiology Collaboration equation) at the Pre-Screening Visit or at any of the Screening Visits;
8. Abnormal urinalysis (defined as proteinuria  $\geq 1+$  or any male or non-menstruating female with  $\geq 1+$  hematuria), with a confirmatory abnormal urine protein:creatinine ratio (e.g.,  $\geq 1+$  proteinurea or hematuria without confirmation by abnormal protein:creatinine ratio will not be an exclusion);
9. Uncontrolled thyroid disease: hyperthyroidism or hypothyroidism as defined by thyroid-stimulating hormone (TSH) below the lower limit of normal or  $> 1.5 \times$  ULN, respectively, based on results from the Pre-Screening Visit or the Screening Visit. If controlled, treatment should be stable for at least 3 months prior to the Screening Visit;

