Any medical condition already present prior to the subject taking the first dose of study drug (Study Day 1) should be reported in the medical history. Any SAEs occurring prior to the first dose of study drug (Study Day 1) should be reported as an update to medical history as well as an adverse event. Any pre-existing medical condition or signs or symptoms that changes in severity, frequency, or seriousness after the subject takes the first dose of study drug (Study Day 1) and through the Follow-up Visit should be reported as an adverse event.

Clinically significant abnormal laboratory values or other examinations (e.g., ECG) that are detected at the time of the first dose of study drug (Study Day 1) and worsen during the study should be reported as adverse events. An abnormal laboratory result that is not verified by repeat testing does not necessitate reporting as an adverse event. The Investigator will exercise his or her medical, scientific, and clinical judgment in deciding whether an abnormal laboratory finding or other abnormal assessment is clinically significant. Clinically significant abnormal laboratory values occurring during the clinical study will be followed until repeat tests return to normal,

stabilize, or are no longer clinically significant. Any abnormal test that is determined to be an error does not require reporting as an adverse event.

An overdose is a deliberate or inadvertent administration of a treatment at a dose higher than specified in the protocol and higher than known therapeutic doses. Overdoses with associated symptoms are always handled as AEs and reported as such. Overdoses without associated symptoms are not reported as AEs but are documented in [specify eg, CRF] in order to collate information for the IB regarding the level of excess dosage taken or administered without adverse effects. An overdose will be reported irrespective of outcome even if toxic effects were not observed.

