##### 8.1.4.3 Possible muscle and liver injury

For muscle injury, CK, hepatic, and renal function laboratory data will be integrated with myopathy signs and symptoms. For management of CK elevations  $> 3 \times$  ULN, refer to [Appendix E](#). For liver injury, laboratory data will be integrated with hepatic signs and symptoms. Alanine aminotransferase increases  $> 2 \times$  ULN with symptoms of hepatitis or  $> 3 \times$  ULN with or without symptoms of hepatitis will be evaluated and managed according to guidelines.

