## **8.6 Clinical Laboratory Evaluations**

Clinical laboratory evaluations will be collected at the visits shown in the Schedule of Procedures ([Appendix A](#)) and the data captured will be forwarded to the central laboratory for evaluation. Assessments that require a subject to fast will be defined as no food or caloric beverage for at least 10 hours prior to sample collection. Subjects will be permitted to have water, black tea or black coffee.

Central laboratory results will be provided to the sites, with the exception of the post-randomization lipid values. TG alert values with a risk mitigation plan is in place with the Central Laboratory ([Section 8.1.4.4 Increased risk for pancreatitis \[TG  \$\geq\$  2000 mg/dL\]](#)). Laboratory results that appear potentially spurious based on the Investigator's clinical assessment and review of the subject's medical history may be repeated for confirmation of the finding. Reassessments of non-qualifying screening labs must be reviewed and approved by the Medical Monitor prior to obtaining the new specimen. The clinical rationale for performing repeat testing of screening assessments should be thoroughly documented.

Standard clinical laboratory evaluations for safety chemistry, coagulation, and hematology will be conducted at all study visits and the Follow-up Visit (only for subjects who had an abnormal result at Week 12 [or the ET Visit, if applicable] or an ongoing treatment-related adverse event). Clinically significant abnormal creatinine results at Week 12 (or the ET Visit, if applicable) will also be followed-up 2 weeks ( $\pm 3$  days) after the last dose of study drug in addition to the 4 week ( $\pm 3$  days) Follow-up Visit. See [Appendix B](#) for a list of clinical laboratory analytes.

A full fasting lipid panel will be assessed at the Pre-Screening Visit, if applicable, and at all other study visits, including the Follow-up Visit. Fasting apolipoproteins and LDL-C (ultracentrifugation) will be assessed at Study Day 1, Week 10, Week 12, the Follow-Up Visit, and the ET Visit, if applicable. In addition to these lipid parameters, hsCRP, IL-6, SAA, and fibrinogen will also be measured at Study Day 1, Week 10, Week 12, and the ET Visit, if applicable. Finally, ANGPTL4, adiponectin and cystatin-C will be measured at Study Day 1 and Week 12 (or the ET Visit, if applicable).

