#### Recommended Hepatic Discontinuation Criteria

Study drug should be discontinued permanently if one of the following occurs (as confirmed by repeat assessment) and if the event is without an alternative explanation:

- ALT or aspartate aminotransferase (AST)  $>8 \times$  ULN;
- ALT or AST  $>5 \times$  ULN for more than 2 weeks;

- ALT or AST  $>3 \times$  ULN and either total bilirubin  $>2 \times$  ULN or international normalized ratio  $>1.5$ ; and/or
- ALT or AST  $>3 \times$  ULN with the appearance of fatigue, nausea, vomiting, right upper quadrant pain or tenderness, fever, rash, and/or eosinophilia ( $>5\%$ ).

It is also recommended that statin regimen is discontinued. Abnormal values should be followed until they return within normal range or to a level deemed acceptable by the Investigator, or until the abnormality is explained by an appropriate diagnosis.

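### Appendix E orders the liver repeat and dosing pause on ALT or hepatitis symptoms only, but its permanent-stop criteria also accept AST and need a confirming repeat, leaving two asymptomatic patterns without a repeat or a pause rule

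*Protocol*

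**What the plan says.** **Evaluation and pause.** In Protocol Appendix E, Hepatic Monitoring, an unscheduled visit follows hepatitis signs or symptoms, ALT above 2 × ULN with symptoms, or ALT above 3 × ULN regardless of symptoms. The text then says: "A repeat assessment should be performed as soon as possible to confirm the finding". On dosing it says: "Study drug should be temporarily discontinued during this evaluation if the subject has signs or symptoms of hepatitis or an ALT" above 5 × ULN. AST is not named in that subsection. Section 8.1.4.3 is also limited to ALT in its liver wording: cases above 3 × ULN "with or without symptoms of hepatitis will be evaluated and managed according to guidelines".

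**Permanent stop.** Under Recommended Hepatic Discontinuation Criteria: "Study drug should be discontinued permanently if one of the following occurs (as confirmed by repeat assessment") and there is no alternative explanation. All four criteria take ALT or AST:

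1. above 8 × ULN;
2. above 5 × ULN for more than 2 weeks;
3. above 3 × ULN with total bilirubin above 2 × ULN or INR above 1.5;
4. above 3 × ULN with listed symptoms and/or eosinophilia above 5%.

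**General provisions.** Appendix E leaves raised hepatic enzymes to standard of care at the investigator's discretion. Section 8.1 adds: "Clinically significant abnormal laboratory values occurring during the clinical study will be followed until repeat tests return to normal", or until they stabilise or lose clinical significance. Section 8.6 says results that look spurious in light of the subject's "medical history may be repeated for confirmation of the finding". Section 4.3 allows withdrawal for a severe laboratory abnormality.

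**AST elsewhere.** Exclusion criterion 4 in Section 4.2 reads "Abnormal liver function test at the Pre-Screening Visit or any of the Screening Visits (aspartate aminotransferase or alanine aminotransferase" above 2 × ULN, so either enzyme excludes. SAP Table 3 flags both enzymes at above 2 and above 3 × ULN.

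**The concern.** A permanent stop on AST cannot take effect until a repeat has been done, yet the paragraph that orders the repeat does not mention AST. A subject without symptoms whose AST is 9 × ULN and ALT 2.5 × ULN has reached a stop threshold, and no specific rule calls that subject back or holds the drug. The same is true of AST 4 × ULN with bilirubin above 2 × ULN.

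The second pattern is milder. A subject with ALT 4 × ULN and bilirubin above 2 × ULN is called back promptly but gets no dosing instruction while the result is pending. A subject with isolated ALT just above 5 × ULN, which alone meets no stop criterion on a single sample, is held.

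What is at stake is the protection of subjects who have reached a written stop threshold. No efficacy analysis, sample size or error rate is involved.

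**Working it through.** The plan gives no figure to reproduce. The check sets the rules side by side, counts the cases they leave open, and derives the time to the next scheduled sample.

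**1. Rules for a subject without symptoms** (Appendix E)

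| Action | Trigger |
|---|---|
| Visit and prompt repeat | ALT > 3 × ULN |
| Temporary pause | ALT > 5 × ULN |
| Stop threshold reached on one sample | ALT or AST > 8 × ULN; or ALT or AST > 3 × ULN with a marker |

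Here a marker means bilirubin > 2 × ULN, INR > 1.5 or eosinophilia > 5%. Criterion 2 is left out because a single value cannot show a duration of more than 2 weeks. For AST it has the same gap, since duration needs a second sample.

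**2. Case count.** Take four bands for each enzyme (≤ 3, > 3–5, > 5–8, > 8 × ULN) and marker yes or no: 4 × 4 × 2 = 32 combinations.

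- Without a marker, a threshold is reached when either enzyme is > 8: 4 + 4 − 1 = 7.
- With a marker, it is reached unless both enzymes are ≤ 3: 16 − 1 = 15.
- Total: 7 + 15 = 22.

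| ALT band | No marker | Marker | Total | Repeat | Pause |
|---|---|---|---|---|---|
| > 5 (two bands) | 5 | 8 | 13 | yes | yes |
| > 3–5 | 1 | 4 | 5 | yes | no |
| ≤ 3 | 1 | 3 | 4 | no | no |

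The split depends on the banding. A finer grid (five bands per enzyme, with separate flags for bilirubin/INR, eosinophilia and duration) gives 134 asymptomatic combinations meeting criteria 1 to 3: 72 with both rules, 26 with a repeat only and 36 with neither. The share with neither is 4/22 = 18% on the first grid and 36/134 = 27% on the second. The two gaps are the same on both grids, and neither share is a patient frequency.

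**3. Time to the next scheduled chemistry, AST pattern only.** Section 6.4 sets Weeks 2, 6 and 10 at Days 15, 43 and 71, each ± 3. For Week 12, Appendix A says: "Week 12 assessments can be performed up to 3 days prior to Study Day 85, but not after Study Day 85". The windows are therefore Days 12–18, 40–46, 68–74 and 82–85.

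| Interval | Nominal | Shortest | Longest |
|---|---|---|---|
| Week 2 to 6 | 43 − 15 = 28 | 40 − 18 = 22 | 46 − 12 = 34 |
| Week 6 to 10 | 71 − 43 = 28 | 68 − 46 = 22 | 74 − 40 = 34 |
| Week 10 to 12 | 85 − 71 = 14 | 82 − 74 = 8 | 85 − 68 = 17 |

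With once-daily dosing, that is about the same number of further doses. These intervals do not apply to the second pattern, where a prompt repeat is ordered.

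**4. How the protocol treats other signals.** Section 8.1.4 orders repeats outright for a hemoglobin fall and for creatinine or GFR changes, and confirmation within 1 week for TG ≥ 2000 mg/dL. An AST rise has no such order.

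**The case against.** The strongest case is that this is guidance, and that judgement fills the space. The stop criteria are headed as recommended, and most of Appendix E is worded as advice. An investigator cannot apply an AST criterion that needs confirmation without repeating the test, so a repeat is implied. Standard of care, follow-up of significant values and discretionary withdrawal all reach AST. These backstops are real, and the 22-to-34-day interval arises only if nobody uses them. Even so, none sets an AST threshold, a time for the repeat, or a hold on AST or bilirubin.

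A second argument is that relying on ALT is a reasonable choice, because isolated AST may come from muscle, statin users are enrolled and Appendix E has a muscle pathway. That pathway does hold drug at CK above 10 × ULN, the only interim hold among the other provisions. It is keyed to CK and muscle symptoms, and does not address AST with raised bilirubin or INR. The plan gives no reason for treating AST differently here when entry, the stop criteria and SAP Table 3 treat the enzymes alike.

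Third, exposure is small: about 90 subjects, 12 weeks of dosing, and entry limits on liver tests and liver disease. Section 1.4 reports 895 exposed subjects with no treatment-related SAE and lists no hepatic event among the most common. This limits the likely number of cases and the weight of the point, but leaves the rules mismatched.

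Finally, a hold on AST above 5 × ULN would sometimes act on muscle-origin AST below the CK thresholds. That is a fair cost.

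**Conclusion.** The concern holds. For subjects without symptoms, Appendix E and Section 8.1.4.3 leave two patterns uncovered:

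- **AST-driven, ALT ≤ 3 × ULN:** a stop threshold can be reached with no specific order for a prompt repeat and no pause.
- **ALT > 3 to 5 × ULN with a marker, or with AST > 8 × ULN:** a prompt repeat is ordered, but there is no instruction to hold drug meanwhile.

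The first is the more important. If no discretionary repeat is done, dosing could run on for the intervals derived above. The second lasts only until the prompt repeat. Elsewhere the triggers are wider than the stop criteria, since symptoms alone or ALT above 3 × ULN alone prompt action.

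The result rests on reading eosinophilia without symptoms as enough for criterion 4, and on treating discretionary provisions as not being rules. The documents give no basis for estimating how often either pattern would occur. This should be fixed as an inexpensive subject-safety correction; it does not threaten the trial's conclusions.

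**What to change.** - In Section 8.1.4.3 and Appendix E, Hepatic Monitoring, key the unscheduled visit and repeat to ALT **or AST** above 3 × ULN. Every stop criterion requires at least this level. Keep the existing symptom triggers.
- In Appendix E, hold study drug at ALT or AST above 5 × ULN, or at any unconfirmed value that reaches a permanent-stop criterion, until the repeat and evaluation are complete.
- Check CK at the same repeat, so that AST of muscle origin is recognised and handled under the muscle-injury rules.

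By construction, all 22 combinations then have both a repeat and a hold. The required analytes (ALT, AST, CK, bilirubin, INR and eosinophils) are already in the Appendix B panels. The cost is a wording change in two places, plus a few extra unscheduled repeats and short dosing holds, some of them for AST of muscle origin.
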